3.1.9 Study Protocol

Participants for this study will be recruited from among UKM undergraduate students at the Kuala Lumpur Campus based on the inclusion and exclusion criteria. Recruitment of volunteers will be conducted through advertisement. Simple random sampling will be used for participant selection, with those meeting the inclusion criteria being eligible for the study, while those meeting the exclusion criteria will be dismissed.

Before the commencement of the clinical trial, all participants will be provided with a consent form to review. The study will take place at the UKM Optometry Clinic, [name], Kuala Lumpur, Malaysia.

Participants will be required to attend the UKM Optometry Clinic for three sessions, each lasting 8 hours, during which they will wear FDA hydrogel contact lenses (groups I, II, III, IV, Va and Vb). Each lens will be placed on one eye only. Hence, the study will involve three wearing sessions, with the first session focusing on groups I and II FDA contact lenses, the second session on groups III and IV FDA contact lenses, and the third session on hydrogel silicone contact lenses Va and Vb. A 2-week rest period will be provided between each session. The complete study procedure is outlined as follows:

Care for Contact Lenses Leaflet.

Ensuring proper hygiene and technique is crucial to prevent eye health complications while wearing contact lenses. Subjects will receive thorough guidance on essential practices, including: maintaining hygiene care, correctly utilizing contact lens solution, applying and removing contact lenses, and adhering to permissible actions during wear. Additionally, subjects will be provided with a hotline for any inquiries or emergencies arising during contact lens use. Furthermore, they will receive a pamphlet titled "Soft Contact Lens Instructions" available at the UKM KL Optometry Clinic.

[figure not shown]

Figure 1 & 2. Soft contact lens use instructions

Pre-Assessment

A pre-assessment will precede the contact lens application during the initial session. The parameters measured will include these three tests: a) assessment of tear quantity using the Schirmer Test, b) evaluation of tear quality with the NIBUT Test, and c) examination of corneal staining using the Efron Grading Scale. These same tests will be conducted after the contact lenses have been worn for 8 hours and subsequently removed.

a) Tear Quantity Assessment (Schirmer Test)

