To assess tear quantity, the Schirmer test will be employed using a 5mm x 30mm Schirmer strip. The strip will be positioned in the temporal area of the subject's lower eyelid. The subject will be instructed to look upwards and blink naturally for 5 minutes, after which the Schirmer strip will be removed. The length of the wet portion of the strip will be measured and documented. Three readings will be obtained in millimeters (mm), and the average reading will be calculated for data analysis (Kallarackal et al., 2002).

b) Tear Quality Assessment (NIBUT Test)

The assessment of tear quality was conducted using the Non-Invasive Break Up Time Test (NIBUT) technique with the Bausch & Lomb keratometer. The subject was instructed to rest their

chin on the designated chin rest and align their forehead with the headrest. Initially, the subject blinked several times and then refrained from blinking. Time was measured from the last blink until the appearance of any distortion or break in the "mires." This time interval was recorded as the NIBUT measurement. If the subject blinked during the measurement, the test was paused briefly, and resumed after a few blinks. A one to two-minute break was provided between each measurement. Three readings were taken, and the average of these readings was utilized for subsequent statistical analysis (Mohidin et al., 2002).

c) Corneal Coloring Assessment (Efron Grading Scale)

The evaluation of corneal staining will involve using the Efron Grading Scale to assess any marks or damage on the subject's cornea before applying contact lenses. Initially, fluorescein dye will be applied to the subject's eyes using fluorescein strips moistened with saline solution. The subject will be instructed to look up, and the moistened fluorescein strip will be gently touched to the lower eyelid, followed by blinking. Using a biomicroscopic slit lamp equipped with a blue cobalt light, any staining or markings on the cornea will be examined. Any observed findings will be documented according to the Efron Grading Scale. Subsequently, the subject's eyes will be rinsed with saline solution to remove the fluorescein dye. The cornea will be divided into five zones (central, superior, inferior, temporal, and nasal) for recording observations, as depicted in Figure 1. The Efron Grading Scale, recognized for its suitability in assessing corneal coloring, will guide the evaluation process (Dundas et al., 2001; Woods & Fonn, 2018).

[figure not shown]

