Figure 3. Grading Scale Based on 5 Corneal Zones

i. Contact lens application

The placement of group I FDA contact lenses will occur on one side of the subject's eye, while group II FDA contact lenses will be positioned on the opposite side, with the positioning being randomized and unknown to the subjects. Researchers will delicately insert the contact lenses, providing clear instructions and precautions to the subjects regarding their wear. Subjects will be advised to remain near the UKM KL Campus throughout the contact lens application and return to the UKM Optometry Clinic after 8 hours for lens removal. Additionally, subjects will be instructed to promptly notify the researcher of any discomfort, pain, or unforeseen issues related to the wearing of contact lenses.

ii. Post-Wear Assessment

The researcher will remove the contact lenses from the subject's eyes. Subsequently, a postwearing examination of the contact lenses will be conducted. This examination mirrors the preuse assessment and includes a) evaluating tear quantity using the Schirmer Test, b) assessing tear quality with the NIBUT Test, and c) grading corneal staining based on the Efron Grading Scale. Following the removal of contact lenses, subjects will be required to complete the Contact Lens Discomfort Index (CLDI) questionnaire twice at each appointment: once for the right eye and once for the left eye. This allows for the measurement of comfort levels separately for each eye.

d) Contact Lens Discomfort Index Questionaires (CLDI)

The CLDI questionnaire will be employed to evaluate the comfort level during the usage of Group I and II FDA contact lenses. This questionnaire's selection of questions is rooted in the Contact Lens Dry Eyes Questionnaire (CLDEQ)-8. Known for its robustness and reliability, the CLDI questionnaire is specifically crafted to gauge comfort levels associated with contact lens wear (Arroyo-del Arroyo et al., 2022).

English version of the contact lens discomfort index (CLDI)

The Contact Lens Discomfort Index (CLDI) questionnaire is an easy instrument to measure the level of discomfort with the contact lenses.

Note: questions highlighted in grey correspond to the subscale score.

- Please, answer the following questions.
- 1. Since you have been wearing this type of contact lens, have you always worn them the same number of hours per day?
 - I currently use them more than previously (0)

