Subjects will be required to attend a second appointment following a rest period for the application of group III and IV FDA contact lenses. This appointment will involve the repetition of the procedure, including pre-application examination, contact lens wear, post-use examination, and subsequent rest period. The same procedure will be replicated for a third appointment involving the wearing of silicone hydrogel contact lenses Va and Vb.

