3.1.10 Flow Chart

3.1.11 Data Analysis

The forthcoming study will employ IBM SPSS Statistics Version 27 for data analysis. The normality of the data will be assessed utilizing the Shapiro-Wilk test. Subsequently, the distribution of the data will be examined accordingly.

Utilize the Paired t-test for normally distributed data or the Wilcoxon signed-rank test for non-normally distributed data to assess the disparities in tear quality and quantity before and after
 Employ the Paired t-test for normally distributed data or the Wilcoxon signed-rank test for non-normally distributed data to compare the mean quality and quantity of tears between FDA contact lens application groups I and II, groups III and IV, as well as silicone hydrogel materials A and B.

iii. Employ the Paired t-test for normally distributed data or the Wilcoxon signed-rank test for non-normally distributed data to assess the comfort levels associated with the application of FDA contact lenses within groups I and II, groups III and IV, as well as silicone hydrogel materials A and B.

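### The between-lens paired tests pool over right and left eye although lens side is randomised; a side-balanced list with a position term would be a cheap gain in precision

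*Protocol*

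**What the plan says.** Each session is a contralateral-eye comparison: "Each lens will be placed on one eye only", with one lens type on each eye. For the first session (FDA groups I and II), section 3.1.9 has the side allocated "with the positioning being randomized and unknown to the subjects". For the second appointment (groups III and IV) it says "This appointment will involve the repetition of the procedure", and it carries the same procedure over to the third (Va and Vb). Randomisation of side in those sessions is therefore implied, though not restated. The protocol does not give the method of randomisation or say whether right and left are balanced.

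Section 3.1.11 names the between-lens tests. For tears it says: "Employ the Paired t-test for normally distributed data or the Wilcoxon signed-rank test for non-normally distributed data to compare the mean quality". That item covers both tear measures and sets the two lenses of a session against each other. The same pair of tests is named "to assess the comfort levels associated with the application of FDA contact lenses within groups I and II, groups III and IV" and for the two silicone hydrogel materials. Neither item mentions the eye. A separate item applies the same tests "to assess the disparities in tear quality and quantity before and after" wear.

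On measurement, the NIBUT description says "A one to two-minute break was provided between each measurement", with three readings averaged. The CLDI is completed separately for each eye at each visit. The order in which the eyes are measured or scored is not given.

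**The concern.** Randomising side splits the subjects of each session into two position groups: first lens on the right eye, or first lens on the left. Every within-subject lens difference then contains the lens effect plus or minus any systematic right-left difference, and the sign is known from the allocation. This is the structure of a two-sequence crossover with eye in place of period. A pooled paired test corresponds to a crossover analysis without the period term: it treats a known component as noise.

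Two things follow if a right-left difference exists. The standard error is larger than it need be. If the sides come out unequal by chance, part of the right-left difference is also added to the observed lens contrast. With 16 to 18 subjects and no stated balancing, unequal splits are likely. Both effects can be avoided with data the trial will have, provided each outcome is recorded by eye.

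**Working it through.** **Inputs from the protocol.** Section 3.1.4 gives 16 subjects plus 2 for dropout, 18 in all. Its own arithmetic reproduces: 1.96 × 0.3 × 0.7 / 0.0025 = 164.64; 10% is 16.46, taken as 16; 16 + 2 = 18. I use 16 completers. The design and tests are as described above.

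**Assumptions.** The protocol states no right-left difference, no lens effect to detect and no significance level for these tests. I take two-sided 5% and a lens effect τ = 0.749 SD, which gives the paired t-test 80% power at n = 16 when d = 0. I vary d, the systematic right-left difference. Units are SDs of the lens difference within a position group.

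**Model.** D = τ + s·d + e, with s = +1 or −1 for position and SD(e) = 1.

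*Error term.* With equal sides the variance of D is multiplied by about 1 + d²: 1.01, 1.06, 1.25 and 2.00 for d = 0.1, 0.25, 0.5 and 1.0.

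*Lens contrast.* The mean of D shifts by d(nR − nL)/n. At 11:5 this is d × 6/16 = 0.375d, that is 0.09 SD at d = 0.25 and 0.19 SD at d = 0.5.

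*Chance of unequal sides.* Under a coin toss for 16 subjects, an exact 8:8 split has probability 19.6%, 10:6 or worse 45.4%, and 11:5 or worse 21.0%. With independent allocation in three sessions, at least one is 11:5 or worse with probability 1 − 0.79³ = 51%.

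**Planned paired t-test, n = 16 (simulated, 100,000 trials per setting)**

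| d (SD) | Type I, coin toss | Type I, 8:8 | Type I, 11:5 | Power, coin toss | Power, 8:8 |
|---|---|---|---|---|---|
| 0 | 5.0% | 4.9% | 5.0% | 80% | 80% |
| 0.1 | 4.9% | 4.9% | 5.1% | 80% | 80% |
| 0.25 | 4.9% | 4.5% | 5.8% | 77% | 78% |
| 0.5 | 4.8% | 3.0% | 7.6% | 71% | 72% |
| 1.0 | 5.1% | 0.6% | 10.0% | 50% | 49% |

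The coin-toss column for type I error describes the test as planned if allocation is simple. The 8:8 and 11:5 columns are conditional on a particular split and average out over the randomisation.

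**With a position term.** The estimate is the mean of the two position-group means. Its standard error is σ√[(1/nR + 1/nL)/4] on n − 2 degrees of freedom. At 8:8 the multiplier is √(0.25/4) = 0.250, the same as 1/√16 for the paired test, so only one degree of freedom is lost. At 11:5 it is √(0.2909/4) = 0.270. Type I error is about 5% for every split tested. Power does not depend on d: 79.6% at 8:8, about 77% averaged over a coin toss, and about 73% at 11:5.

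**Comparison.**
- 8:8 sides: the term changes power from 80.0% to 79.6% at d = 0, and from 72% to 80% at d = 0.5.
- Coin toss: the term changes power from 80% to 77% at d = 0, breaks even at about d = 0.3, and gains about 6 points at d = 0.5 (71% to 77%).
- 9:9 sides with 18 completers: the term costs about 0.3 points at d = 0 and gains about 6 points at d = 0.5 (78% to 85%).

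**The case against.** The strongest reply is that nothing here is an error. Side is randomised within the subject, so a right-left difference is zero on average in the lens contrast, and a paired test is valid without an eye term. That stands. A reader who looks only at the 11:5 column might infer that the planned test has an inflated error rate. The documents do not support this: over simple randomisation type I error is about 5% at every d tested, and no text says that sides will be unequal.

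Second, a reader might infer from the breaks between NIBUT readings and the two CLDI forms that the second eye is always measured minutes later, or that the right eye is always scored first. The protocol states neither. An order effect behaves like a side effect only if order is tied to side, so it is a possibility and not a finding.

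Third, the size of d has no basis in the protocol. At 0.25 SD or less the loss is negligible to small. This also stands.

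Fourth, the eye term is not free. Under unbalanced allocation it costs about 3 points when d = 0, and at 11:5 about 7 (80% to 73%). This stands as well, and it is the reason to tie the term to a balanced list.

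Fifth, the point does not reach the before/after tests: taken within the same eye, they cancel a stable right-left difference.

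Last, an analysis plan that is not shown may add an eye term or a balanced list. That is possible, but section 3.1.11 itself names the tests, so it is fair to comment on the choice it states.

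**Conclusion.** The point holds as a minor matter of efficiency, confined to the between-lens comparisons of tears and comfort. The planned tests are valid over the randomisation. They leave any systematic right-left difference in the error term and let it shift the observed contrast when sides are unequal by chance. The cost is at most about 3 power points for d up to 0.25 SD and about 8 to 9 points at 0.5 SD. These figures rest on 16 completers, a two-sided 5% level, a lens effect of 0.749 SD, approximately normal differences, and values of d that are assumed throughout. The gain is clear only from about 0.5 SD if sides are left to a coin toss; with balanced sides there is almost nothing to lose at any d.

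**What to change.** For the between-lens comparisons only:

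1. Balance lens side within each session by a blocked list (9:9 for 18 subjects), and state that this applies to all three sessions.
2. State the order in which the two eyes are tested and the CLDI forms completed: either fix it or randomise it, and record it.
3. Regress the within-subject lens difference on a position indicator coded +1/−1 and test the intercept. For non-normal outcomes use a position-stratified rank or permutation version, for instance a rank-sum test of the right-minus-left differences between the two position groups.

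The cost is one list, one recorded item and one degree of freedom: about 0.4 power points at n = 16 with equal sides if there is no right-left difference, against a gain of about 7 points at 0.5 SD (80% versus 72%). No extra measurements are needed if every outcome is recorded by eye. Steps 1 and 3 should be adopted together, because the term without balancing costs about 3 points on average when d = 0. The before/after tests need no change on this account.

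### Masking to lens position is stated for the subjects only; the reader of NIBUT and corneal staining is neither named nor masked, so examiner expectation can bias the between-lens comparison

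*Protocol*

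**What the plan says.** All of the relevant text on conduct is in Protocol section 3.1.9.

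- **Masking.** The part on contact lens application places one lens of the pair on each eye, "with the positioning being randomized and unknown to the subjects". This is the only masking statement in the protocol. It is written for the Group I/II session. The second and third appointments repeat the procedure, and randomisation and masking are not restated for them.
- **Handling.** "Researchers will delicately insert the contact lenses". After wear, "The researcher will remove the contact lenses from the subject's eyes".
- **Post-wear readings.** The sentence after removal reads "Subsequently, a postwearing examination of the contact lenses will be conducted". It is in the passive voice and names no assessor. The timing is clear: "These same tests will be conducted after the contact lenses have been worn for 8 hours and subsequently removed".
- **Nature of the readings.** For NIBUT, "Time was measured from the last blink until the appearance of any distortion or break" of the keratometer mires. For staining, the cornea is viewed at the slit lamp and "Any observed findings will be documented according to the Efron Grading Scale".

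Section 3.1.11 Data Analysis then compares tear quality and quantity between the two lenses of each pair, by paired t-test or Wilcoxon signed-rank test.

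**The concern.** In this contralateral design, two lenses are compared within one person on one day. An examiner who knows which eye wore which lens, and who expects one of them to do worse, may call the mires distorted a little earlier or choose a higher staining grade for that eye. That error follows the lens, not the eye. Randomising the eye balances right-left differences but leaves a lens-linked error fully in the paired difference.

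The protocol itself contains grounds for such expectations. Section 2.1 Literature Review describes Group I as the most stable group and Group IV as more reactive, and reports a 2-3 times higher likelihood of dry eyes with Groups II and IV than with Group I.

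At stake is whether a NIBUT difference between paired lenses can be attributed to the lenses. Readings taken unmasked cannot be corrected by later analysis. Who is masked is a matter of conduct that belongs in the protocol, and the protocol has settled it for the subjects only.

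**Working it through.** **Step 1: who knows what, from section 3.1.9.**

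| Role | Named? | Masked to lens position? |
|---|---|---|
| Subject | yes | yes |
| Person inserting | researchers (plural) | not stated |
| Person removing | the researcher | not stated |
| Person reading NIBUT and staining after wear | no | not stated |

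The protocol describes no coded lenses, no concealed key and no separation between handling and measuring. Followed as written, it permits an unmasked reader.

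**Step 2: which analyses are exposed.**

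- NIBUT: observer-read, with a between-lens paired test in section 3.1.11. Directly exposed.
- Staining: observer-graded. Section 3.1.11 names no test for it, so exposure arises only if the grades are compared between lenses.
- Before versus after wear: the stage is known to any reader, so masking lens position cannot act on this comparison.

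**Step 3: size, for NIBUT only.** The protocol gives no figure for examiner bias, so there is none to reproduce. The bias below is an assumption, shown as a range.

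Inputs: n = 16 pairs (section 3.1.4, before the dropout allowance); two-sided 5% paired t-test (the 5% level is an assumption); true difference zero; bias b in SDs of the paired difference.

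The test statistic follows a noncentral t distribution with n − 1 = 15 degrees of freedom and noncentrality b × √n = 4b. The critical value is 2.131. The false-positive rate is P(|T| > 2.131).

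| Assumed bias b | Noncentrality 4b | False-positive rate |
|---|---|---|
| 0 | 0 | 5.0% |
| 0.1 | 0.4 | 6.6% |
| 0.25 | 1.0 | 15.5% |
| 0.5 | 2.0 | 46.5% |

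With all 18 subjects, the three biased rows become about 6.9%, 17% and 51.6%. A larger sample makes a fixed bias more, not less, likely to be declared significant.

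The calculation is not carried over to staining: the Efron grade is ordinal and no test is specified for it.

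**Step 4: can the reader be masked?** The post-wear tests follow lens removal, so no lens is on the eye to reveal the group during the readings. The protocol refers to researchers in the plural, which makes a split of roles plausible. It does not give staff numbers, packaging, tint or other visible lens features, so feasibility is likely but not shown.

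**The case against.** The strongest reply is that the protocol is silent rather than wrong. A reader might infer that the researchers who insert and remove the lenses also take the readings, and that they know each lens's group. The first is the natural reading of consecutive sentences, but the examination is in the passive voice and the protocol does not say what the inserting researcher knows. Neither is established. The weakness does not depend on either: nothing in the text prevents an unmasked reader, and no other assessor is described.

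A reader might also take staining to be exposed in the same way as NIBUT. The documents do not support that. Section 3.1.11 specifies no between-lens test for staining, and objective ii in section 2.6.2 frames the staining contrast as pre- and post-wear. The figures above therefore apply to NIBUT alone.

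Three further objections stand:

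- The stated research question and hypothesis (sections 2.3 and 2.4) concern before versus after wear, which masking of lens position does not protect.
- The bias sizes have no anchor in the protocol. They run from negligible to severe and do not show that bias of any size will occur.
- It is not shown that masking needs no extra assessor. Moving lenses into other cases could also change their storage solution, which matters because section 2.1 mentions possible effects of solution pH on Group IV lenses. The remedy has to avoid that.

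**Conclusion.** The point holds in limited form. Section 3.1.9 masks the subjects only and neither names nor masks the reader of two observer-judged outcomes. Examiner expectation can therefore bias the within-session NIBUT comparison, and any between-lens reading of staining, in all three sessions if the second and third repeat the first. Randomising the eye is no protection.

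The size is unknown. The range of about 6.6% to 46.5% rests on an assumed bias of 0.1 to 0.5 SD, 16 pairs, a two-sided 5% paired t-test and no true difference. It illustrates how a lens-linked error acts; it does not estimate one. The change is worth making because it is cheap and the bias cannot be repaired after the readings are taken.

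**What to change.** State in section 3.1.9 who reads NIBUT and staining, and that this person is masked to lens position in all three sessions. A workable procedure with the existing team:

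1. One researcher prepares the randomised lenses and over-labels them with subject number, session and R/L only, leaving each lens in its own storage solution.
2. That researcher keeps the key closed until the session's readings have been entered.
3. Where two researchers attend, the one who handles the lenses does not take the readings.

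The cost is some preparation time, an added labelling step and a closed list; no extra visit or measurement is needed. Masking may be only partial if a lens can be recognised by its appearance, and feasibility depends on staffing and lens features that the protocol should confirm. It should also acknowledge that before-versus-after readings remain unmasked as to stage.

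### The test order listed in 3.1.9 puts Schirmer strips ahead of every NIBUT reading, and the time from lens removal to post-wear NIBUT is not fixed

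*Protocol*

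**What the plan says.** Protocol section 3.1.9 introduces its steps with "The complete study procedure is outlined as follows". The pre-wear list is "a) assessment of tear quantity using the Schirmer Test, b) evaluation of tear quality with the NIBUT Test", followed by corneal staining, and the three tests are then described in that order. After wear: "The researcher will remove the contact lenses from the subject's eyes. Subsequently, a postwearing examination" follows, which is said to mirror the pre-wear one and "includes a) evaluating tear quantity using the Schirmer Test, b) assessing tear quality with the NIBUT Test, and c) grading corneal staining". For the later sessions, "This appointment will involve the repetition of the procedure".

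For Schirmer, the subject is to "look upwards and blink naturally for 5 minutes, after which the Schirmer strip will be removed", and three readings are averaged. For NIBUT, three readings are averaged with 1-2 min between them. The lenses of a session go one to each eye, "with the positioning being randomized and unknown to the subjects".

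The Introduction (2.0) prefers NIBUT because it studies tear stability with nothing placed in the eye. Its explicit contrast is with the fluorescein break-up test. Section 3.1.11 plans paired before-after tests of tear quality and paired comparisons between the two lenses of a session.

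The visible text does not call the letters a running order. It sets no interval from lens removal to NIBUT and no pause after Schirmer, and it does not say whether the eyes are tested together or in turn. The content of the flow chart in 3.1.10 is not visible.

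**The concern.** Two things follow if staff work down the list.

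- NIBUT, chosen because it leaves the tear film undisturbed, is read just after paper strips have been in contact with the eye.
- Post-wear NIBUT is read some time after the lens has come out. If the lens effect on tear stability is short-lived, part of it may be gone by then, and the before-after contrast in 3.1.11 would be diluted. NIBUT is the only tear-quality measure in the study.

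Because the interval is not fixed, it could also vary between subjects, sessions and eyes. Test order and timing are procedure at the visit; an analysis plan cannot recover an interval that was neither fixed nor recorded.

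**Working it through.** The protocol states no removal-to-NIBUT time, so there is no figure to reproduce. The check is elapsed-time arithmetic.

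**Inputs, all from 3.1.9:** 5 min per Schirmer strip; three Schirmer readings; three NIBUT readings with 1-2 min between them, so 2 breaks x 1-2 min = 2-4 min per eye plus reading time. **Assumption:** three readings means three separate strips. The protocol does not say so, and the one-strip case is shown as well.

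**Minutes from lens removal to the first post-wear NIBUT reading, if the list is followed:**

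| Reading of the protocol | Arithmetic | Result |
|---|---|---|
| Three strips, both eyes together | 3 x 5 | 15 |
| One strip read three times, both eyes together | 1 x 5 | 5 |
| Three strips, eyes in turn, all Schirmer first | 2 x 15 | 30 (first eye) |
| Three strips, one eye finished before the other | 15 + (2-4) + 15 | 15 (first eye), 32-34 (second eye) |
| One strip, one eye finished before the other | 5 + (2-4) + 5 | 5 (first eye), 12-14 (second eye) |

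None of these is a ceiling: strip changes, handling and any rests between strips would add to them.

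**Pre-wear against post-wear.** With three strips and both eyes together, the Schirmer block ahead of NIBUT is 15 min before wear and 15 min after wear, a difference of 15 - 15 = 0 min. What differs is the time since a lens was in the eye. Post-wear it is the figure in the table. Before wear no lens has just been removed: 3.1.6 asks for at least 2 weeks without lenses before the trial, and 3.1.9 gives a 2-week rest between sessions.

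**If NIBUT comes first.** The Schirmer part of the delay falls to 0 min, leaving handling time and NIBUT's own breaks. Schirmer starts 2-4 min later if NIBUT readings alternate between the eyes, or 2 x (2-4) = 4-8 min later if the eyes are done in turn, plus reading time. With both eyes' strips together, the midpoint of the three strips moves from 15 / 2 = 7.5 min after removal to 7.5 + (2-4) = 9.5-11.5 min, or to 7.5 + (4-8) = 11.5-15.5 min.

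**The case against.** **The order is inferred.** The lists say what the examination includes; they do not say in this order, and the flow chart may show a sequence. This stands, and it makes the point conditional. Even so, the same order appears in both lists and in the test descriptions, under wording that promises the complete procedure, so staff would naturally follow it.

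**No effect on a result is shown.** Dilution requires the lens effect on NIBUT to fade soon after removal, and the protocol gives no recovery rate. This stands. Only minutes can be computed.

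**Schirmer first may be deliberate.** Section 2.2 names tear quantity after 8 hours of wear as the gap, and specific objective i names tear quantity. Whether the blink-holding in NIBUT affects a later Schirmer reading is not settled by the protocol either. The trade-off is real but small: a shift of 2-8 min plus reading time, in a measurement that three strips already spread over 15 min.

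**The fit with the Introduction is only partly poor.** Its explicit contrast is with fluorescein, and the listed order does keep NIBUT ahead of fluorescein. That is correct. The broader reason given there, a test with nothing put in the eye, still sits badly with strips placed first.

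**Stronger readings that do not hold.** A reader might infer that post-wear NIBUT waits 15 min longer than pre-wear NIBUT. It does not, because the same Schirmer block comes first both times. A reader might also infer that strip disturbance biases the paired comparisons. It is common to both time points and both eyes, so it need not. Nor does the delay by itself bias the between-lens comparison. Testing both eyes together makes the lag equal. Testing them in turn makes it unequal, but that adds noise rather than systematic bias as long as eye order is independent of the randomised lens placement.

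**Conclusion.** The point holds in a limited form and is worth considering. As listed, 3.1.9 puts Schirmer strips before every NIBUT reading and leaves the lens-free time before post-wear NIBUT open: about 15 min with three strips and both eyes together, 5 min with one strip, and 30 min or more if the eyes are done in turn. The possible consequence is a diluted before-after NIBUT contrast.

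This rests on three assumptions: that staff follow the list, that the flow chart does not say otherwise, and that the lens effect fades soon after removal. The protocol supports no figure for the size of any effect and does not show that one exists.

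**What to change.** State in 3.1.9, and make the flow chart in 3.1.10 agree:

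- At every session, before and after wear, the tests are done in the order NIBUT, then Schirmer, then fluorescein staining.
- Post-wear NIBUT starts as soon as possible, at a standard time after lens removal that is the same for both eyes as far as practicable.
- The order in which the eyes are tested does not depend on the lens worn.

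This re-orders existing tests and needs no extra procedure or staff. The cost is the later Schirmer start worked out above, which lengthens the lens-free time before the tear-quantity measurement by the same amount.
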